2.0 BACKGROUND AND RATIONALE

2.1 Background

Advancements in the treatment of acute lymphoblastic leukemia (ALL) have pushed the cure rate to greater than 90%.¹ Intensifying glucocorticoid use (i.e. prednisone and dexamethasone) has been key in accomplishing these outcomes. However, glucocorticoid-induced osteonecrosis (ON) is one of the most common dose-limiting toxicities of ALL therapy in children.²⁻⁶ Symptomatic cases (defined as Common Terminology Criteria for Adverse Events (CTCAE) grade 2-4) often occur during the first two years of treatment, and may result in early discontinuation of glucocorticoids from treatment. Age is the most significant risk factor, with ALL patients greater than 10 years of age at higher risk of developing ON.^{2,3,5,6} The most common affected joints are the hip, knee, and shoulder.⁷⁻⁹ In both Total XV³ and Total XVI¹⁰, the rate of symptomatic osteonecrosis in children age 10 or older was ~40%.

Recent work has demonstrated that patients with ALL age 10 or older at diagnosis who develop hypertension during glucocorticoid containing phases of therapy were more likely to develop osteonecrosis. Among 235 children treated on Total XV and Total XVI, osteonecrosis occurred in 52% of the 94 who developed hypertension compared to 38% of those who were normotensive [p=0.037, odds ratio (OR) 1.75, 95% confidence interval (95% CI) 1.02-3.01].¹¹ The association was maintained in a multivariable analysis of all known factors associated with either hypertension or osteonecrosis (p=0.03, OR 1.88, 95% CI 1.1-3.22). When the analysis was restricted to osteonecrosis that developed during protocol therapy, 52% of patients with hypertension developed osteonecrosis compared to 34% of normotensive patients (p=0.006, OR 2.11, 95% CI 1.2-3.6). Hypertension was also associated with an increased frequency of extensive epiphyseal involvement ($\geq 30\%$ of the surface effected) of the hip and knee joints on screening MRIs; this is significant as this degree of involvement is associated with joint collapse and the need for surgical intervention.^{12,13}

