4.0 TREATMENT PLAN

4.1 Treatment

Following enrollment and randomization, a target systolic blood pressure range will be chosen for each participant based on their randomization arm, age, sex, and height. Target blood pressures for girls randomized to standard and intensive blood pressure control are shown in Tables 1a and 1b, respectively. Target blood pressures for boys randomized to standard and intensive blood pressure control are shown in Tables 2a and 2b, respectively. For patients ages 10-12 years, select the height column closest to their true height. If two columns are equidistant from their true height, select the lower height.

Patient randomization will be stratified based on patient’s location (Memphis vs. other), use of antihypertensives prior to randomization, and factors known to influence osteonecrosis risk, specifically sex and self-declared race (non-Hispanic white vs. other).

Patients will begin antihypertensive therapy to achieve the targeted blood pressure on day 4. Patients already receiving antihypertensive therapy prior to day 4 should have their therapy adjusted according to the guidelines below. **Patients requiring an antihypertensive should be started on lisinopril** (initial dose 2.5mg daily) unless there is a contraindication to its use. Lisinopril dose may be escalated as indicated. Recommended second line agents for use when lisinopril is contraindicated include angiotensin receptor blockers (e.g. losartan 25mg daily), beta-blockers (e.g. carvedilol 3.125mg BID or, if cardiac rate control is required, metoprolol 12.5mg BID) or a calcium channel blocker (e.g. amlodipine 2.5mg daily).

Table 1a: Girls’ Standard Arm Systolic Blood Pressure Targets							
Age/Height (cm)	Height 5%	Height 10%	Height 25%	Height 50%	Height 75%	Height 90%	Height 95%
10 years	130 cm	132 cm	136 cm	141 cm	146 cm	150 cm	153 cm
Standard Low End Target (mmHg)	109	110	111	112	113	115	116
Standard High End Target (mmHg)	113	114	114	116	117	119	120
11 years	136 cm	138 cm	143 cm	148 cm	153 cm	157 cm	160 cm
Standard Low End Target (mmHg)	111	112	113	114	116	118	120
Standard High End Target (mmHg)	115	116	117	118	120	123	124
12 years	143 cm	146 cm	150 cm	155 cm	160 cm	164 cm	166 cm
Standard Low End Target (mmHg)	114	115	116	118	120	122	122
Standard High End Target (mmHg)	118	119	120	122	124	125	126
13+ years	All heights						
Standard Low End Target (mmHg)	130						

Standard High End Target (mmHg)	135						

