10.2 Randomization

Open-label, stratified block randomization with block size of 4³⁹. Randomization will be stratified by site (SJCRH and other), gender, self-declared race/ancestry (White Non-Hispanic and other) and hypertension requiring >1 dose of medication before Day 4 (Yes/No).

Analyses for the primary and secondary objectives will not be stratified. If it is determined that certain important factors are not balanced between the two treatment arms, appropriate regression models (such as logistic or integer response models) will be applied. The power assessment below is based on an unstratified Chi-square test.

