10.4 Primary Objective

To compare the frequency of radiographically significant osteonecrosis in patients receiving intensive compared to conventional antihypertensive therapy.

The primary endpoint is the number of major joints (hips and knees) with extensive epiphyseal osteonecrosis ($\geq 30\%$ affected surface^{12,13,17}) on MRI after approximately 9 months of chemotherapy (during reinduction 2). All randomized patients with appropriate imaging are considered evaluable and all analyses will be done according to intent-to-treat.

A chart review of 140 TOTXVI patients meeting the eligibility criteria of this study showed the following distribution of the number of affected joints in the low BP within-target group vs. the above-target group:

	Number of affected joints					Total
	0	1	2	3	4	
Above-target (proportion, n)	0.583, 70	0.083, 10	0.233, 28	0.017, 2	0.083, 10	120
Within-target (proportion, n)	0.80, 16	0.05, 1	0.10, 2	0.00, 0	0.05, 1	20

Clearly in each BP group the distribution is bi-modal with local modes at 0 and 2.

The primary analysis will consist of two parts. In the first part the distribution of the number of affected joints will be compared by the exact one-sided Chi-square test comparing the probability of having at least 1 affected joint. Let $P_0(k)$ and $P_1(k)$ be the probability of k affected joints among patients above- and within-target respectively ($k=0,1,2,3,4$). We have noted in the preliminary data that the BP of 14.6% of the eligible patients was within target without any treatment. Therefore, the distribution of the number of affected joints in the control group is anticipated to be $PC(k)=0.854*P_0(k)+0.146*P_1(k)$, and the distribution in the treatment group is anticipated to be $PT(k)=P_1(k)$, $k=0,1,2,3,4$. Applying the preliminary data displayed above to this model, we obtain the anticipated distribution in the control and treatment group as follows:

	Number of affected joints k	
	0	1+
Control	0.615	0.385
Treatment	0.8	0.2

With $n=80$ subjects per group, the one-sided test has the exact power of 78.7% to detect the above anticipated difference at the 5% significance level. The power is calculated using Cytel Studio II.

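### The osteonecrosis tests ignore sex and race, which the plan randomises by and calls osteonecrosis risk factors; a stratified exact test would recover a little power at almost no cost

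*Combined protocol and SAP*

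**What the plan says.** Section 10.2 (Randomization) uses blocks of 4 stratified by site, sex, race and prior hypertension treatment, each with two levels, which gives 2 × 2 × 2 × 2 = 16 strata. Section 4.1 (Treatment) gives the reason for two of them: they are "factors known to influence osteonecrosis risk, specifically sex and self-declared race".

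On analysis, section 10.2 states: "Analyses for the primary and secondary objectives will not be stratified". It adds: "The power assessment below is based on an unstratified Chi-square test". Adjustment enters by one route only, a conditional clause: if "certain important factors are not balanced between the two treatment arms, appropriate regression models (such as logistic or integer response models) will be applied".

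In section 10.4, the first part of the primary analysis is the "exact one-sided Chi-square test comparing the probability of having at least 1 affected joint". Section 10.5 tests Grade 2+ osteonecrosis with a similar one-sided two-by-two chi-square test. By contrast, the blood-pressure model in section 10.5 includes age, sex and race.

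**The concern.** The plan treats sex and race as important enough to balance at randomisation because they affect the endpoint, and then leaves them out of the test of that endpoint. When randomisation is balanced on a prognostic factor and the test ignores it, the test still counts the between-stratum variation as noise. It rejects too rarely under the null and loses some power under the alternative. The data needed to avoid this are collected at randomisation, and planned power is already below 80%.

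The imbalance clause does not fill the gap. It names no factors, sets no size of imbalance and does not state the standing of the regression. Because randomisation is blocked on sex and race, it would also seldom be triggered by a large imbalance in either of them.

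**Working it through.** **Inputs from section 10.4.** 80 patients per arm, one-sided 5% level, treatment rate 4/20 = 0.20. Control rate = 0.854 × 50/120 + 0.146 × 0.20 = 0.3558 + 0.0292 = 0.385.

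**The plan's own figure.** Power is the sum of Bin(x; 80, 0.385) × Bin(y; 80, 0.20) over all pairs (x, y) for which the one-sided Fisher p-value is at most 0.05. This gives 78.66%, against the stated 78.7%, so the figure is correct. At a common rate of (0.385 + 0.20)/2 = 0.2925, the same rejection region has size 3.56%.

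**Assumptions, because the documents give no stratum effects.** Prevalences: sex 45%, race 55%, prior treatment 30%, site 50%. Sex and race each carry the same odds ratio (OR), between 1 and 3. Overall rates are held at 0.385 and 0.20 for power, and at 0.2925 in both arms for size.

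**Simulation.** 20,000 trials per scenario, with 180 patients randomised in 16 strata with blocks of 4, 20 lost at random and 160 analysed. The stratified test takes the total number of control-arm events over the four sex-by-race cells. With each cell's margins fixed, its null distribution is the convolution of four hypergeometric distributions, and p is the upper tail. Monte Carlo standard error is about 0.28 points for power and 0.13 for size.

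| OR for sex and race | Power, planned exact (%) | Power, exact 4 cells (%) | Gain (points) | Size, planned (%) | Size, 4 cells (%) |
|---|---|---|---|---|---|
| 1 | 78.4 | 78.3 | −0.1 | 3.7 | 3.7 |
| 1.5 | 78.7 | 78.9 | +0.2 | 3.4 | 3.4 |
| 2 | 78.8 | 79.9 | +1.1 | 3.2 | 3.4 |
| 3 | 79.4 | 81.8 | +2.4 (+2.5 before rounding) | 2.8 | 3.3 |

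A separate simulation of 8,000 trials per scenario gave gains of about 0, +0.4, +1.3 and +2.8 points. At OR 3 it gave sizes of 2.9% (planned) and 3.3% (stratified).

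**Cell sizes.** The smallest cell is expected to hold 160 × 0.45 × 0.45 = 32.4 patients. The simulated average minimum is 30.8, with about 8–9 events in that cell. The fewest events in any of the four cells, which need not be the smallest cell, is about 4–8. The four-cell test is therefore not sparse.

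**When the imbalance clause would act.** The plan sets no threshold, so two are shown. Sex or race differs between arms by 5 points in about 25% of trials and by 10 points in about 0.5%. A single unstratified factor with 50% prevalence does so in about 53% and 20–21%. The clause therefore bears mainly on factors outside the randomisation.

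**The case against.** The strongest reply is that this is a disclosed and valid choice. Stratifying the randomisation and testing without strata is not a contradiction. Section 10.2 says plainly that both the analysis and the power are unstratified, and the test holds its level. All of that stands.

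The reply also says that the gain is near zero unless strong effects are assumed. That stands in part: at OR 1.5 the gain is only a few tenths of a point, and 2.5–3 points requires OR 3 for both factors. The OR of 1.75 in section 2.1 concerns hypertension during therapy, a different exposure and endpoint, so it cannot narrow the range. What remains is that the change costs almost nothing and uses factors that the plan itself calls prognostic.

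A reader might infer from the imbalance clause that the plan leaves the primary result undetermined. The text does not support that. Section 10.4 designates the exact one-sided test as the first part of the primary analysis and does not list the regression there. The clause lacks detail, but it does not displace the primary test.

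A reader might also point to section 2.1, which says "Age is the most significant risk factor", and treat the absence of age as a serious omission. That contrast is around age 10, and every participant is 10 or older, so the documents do not show how strongly age matters within this trial.

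Finally, section 10.4 also estimates and compares mean joint counts. A proposal that covers only any affected joint would be incomplete.

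**Conclusion.** The point holds as a small loss of efficiency, minor to modest in weight. With the planned exact test, about 0, 0.2–0.4, 1 and 2.5–3 power points are given up at odds ratios of 1, 1.5, 2 and 3 for sex and race. Size drifts from about 3.6% to about 2.9%. These figures rest on the assumed prevalences and odds ratios above.

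A reader might infer that ignoring the strata inflates type I error or that the power is misstated. Neither is so: the error is on the conservative side, and 78.7% is correct for the test described.

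Two nearby inconsistencies are separate and lend this point no support. The fourth stratification factor is "use of antihypertensives prior to randomization" in section 4.1 but "hypertension requiring >1 dose of medication before Day 4" in section 10.2. Section 2.2 says that dexamethasone duration will be considered as a covariate for symptomatic osteonecrosis, while the Grade 2+ test in section 10.5 has no covariate.

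**What to change.** 1. In sections 10.2 and 10.4, make the primary test a one-sided exact stratified (exact Cochran-Mantel-Haenszel) test over the four sex-by-race cells at the 5% level. Report a stratified risk difference with a confidence interval.
2. Test Grade 2+ osteonecrosis in section 10.5 the same way.
3. Keep the unstratified exact test as a sensitivity analysis.
4. Replace the imbalance trigger with one pre-specified supportive regression on the randomisation factors, stated not to replace the primary test: logistic for any affected joint. If the joint-count comparison in section 10.4 is also adjusted, use the same factors.
5. As separate tidying, reconcile sections 4.1 and 10.2 on the fourth stratification factor, and sections 2.2 and 10.5 on dexamethasone duration.

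The cost is SAP wording, simple programming and a reworded power statement. No new data are needed. If sex and race are not prognostic, about 0.1 power point is lost. The test should stay exact. The asymptotic version shows 82.9% power instead of 78.3% at OR 1, but that gain comes from leaving the exact test, not from stratifying, and it gives up the guaranteed 5% level.

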10.3 Monitoring

To monitor the safety of therapy intensification, we will monitor for the following targeted toxicities: acute kidney injury (CTCAE grade 3 or higher not resolving to grade 0-1 within 72 hours) and syncope resulting in any injury. We will count events occurring during glucocorticoid containing phases only.

The intensive BP control arm (experimental) will be closely monitored for adverse effects and clinically suboptimal efficacy. The monitoring rules are constructed according to the Binomial group sequential design. We shall suspend the trial and investigate if any threshold defined in the rules is crossed.

AE monitoring in the intensive treatment arm: Probabilities of suspending trial to monitor > 25% targeted AE:

	True targeted AE probability			
	0.20	0.25	0.30	0.35
Suspend if number of AEs >7/20	0.03	0.07	0.23	0.40
Suspend if number of AEs >13/40	0.01	0.03	0.14	0.22
Suspend if number of AEs >25/80	0.00	0.01	0.12	0.18

Monitoring of missing the target in the intensive treatment arm: against <70% Probability of stopping

	True success probability			
	0.55	0.60	0.70	0.75
Suspend if number of successes <12/20	0.59	0.40	0.11	0.04
Suspend if number of successes <24/40	0.17	0.13	0.07	0.03
Suspend if number of failures <51/80	0.19	0.24	0.04	0.00

Efficacy monitoring of failures at reinduction II MRI (failure defined as $\geq 30\%$ involvement in any joint) against >50% failure rate.

	True success probability				
	0.35	0.40	0.45	0.50	0.55
Suspend if # successes <7/20	0.42	0.25	0.13	0.06	0.02
Suspend if # successes <16/40	0.31	0.23	0.13	0.05	0.01
Suspend if # successes <33/80	0.17	0.17	0.08	0.02	0.00

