Brief Outline of Treatment Plan: Patients will be randomized on day 4 of induction therapy to either conventional or intensive blood pressure goals. Patients will be treated with the long-acting antihypertensive lisinopril to achieve blood pressure control as indicated by their randomized arm. Long-acting therapy will be adjusted every 3-4 days as needed to achieve targeted control based on the median of blood pressures obtained in that period. Treatment of hypertension to the target will continue until the completion of reinduction II therapy. Patients will be evaluated for osteonecrosis as indicated in their primary therapeutic protocol using MRI during reinduction II.
Study Design: Randomized unblinded trial of conventional vs. intensive hypertensive control. Evaluation of the MRIs defining the primary endpoint will be performed by a blinded radiologist.
Sample Size: We will randomize 160 evaluable patients (180 total).
Data Management: Data management and statistical analysis will be provided locally by the Comprehensive Cancer Center Hematological Malignancies Program and the Biostatistics Department at St. Jude Children’s Research Hospital.
Human Subjects: The risks to subject will be related to the toxicity of antihypertensive therapy. Side effects are anticipated to be mild and limited to reversible orthostatic/postural hypotension and transient increases in creatinine. Patients will be informed of this and other minor side effects during informed consent discussion. Adverse events will be monitored and reported and treated appropriately.

TABLE OF CONTENTS

1.0	OBJECTIVES	1
1.1	Primary Objective	1
1.2	Secondary Objectives	1
1.3	Exploratory Objectives	1
2.0	BACKGROUND AND RATIONALE	2
2.1	Background	2
2.2	Rationale	2
2.3	Background and Rationale for Ancillary and Exploratory Studies	3
3.0	RESEARCH PARTICIPANT ELIGIBILITY CRITERIA AND ENROLLMENT	4
3.1	Inclusion Criteria	4
3.2	Exclusion Criteria	4
3.3	Research Participant Recruitment and Screening	5
3.4	Enrollment on Study at St. Jude	5
3.5	Enrollment Instructions for Collaborating Sites	5
4.0	TREATMENT PLAN	6
4.1	Treatment	6
4.2	Participation of St. Jude Affiliates in the Treatment Plan	9
4.3	Treatment Modifications for Collaborating Sites	9
4.4	Supportive Care	9
4.5	Symptom Survey and Semi-structured Interviews	10
5.0	REQUIRED EVALUATIONS, TESTS, AND OBSERVATIONS	12
5.1	Pre-Study Evaluations	12
5.2	Evaluations during Therapy	12
5.3	Response Evaluations	13
5.4	Off-Study Evaluations	13

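### The toxicity rule in 10.3 watches the intensive arm alone against an unexplained 25% ceiling; the basis for 25% should be stated and a between-arm trigger added beside the rule

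*Combined protocol and SAP*

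**What the plan says.** Section 10.3 (Monitoring) says it monitors the safety of therapy intensification. The targeted toxicities are "acute kidney injury (CTCAE grade 3 or higher not resolving to grade 0-1 within 72 hours) and syncope resulting in any injury", and on the window it says: "We will count events occurring during glucocorticoid containing phases only".

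The design and the action are stated as "The monitoring rules are constructed according to the Binomial group sequential design" and "We shall suspend the trial and investigate if any threshold defined in the rules is crossed". The toxicity table is headed "AE monitoring in the intensive treatment arm: Probabilities of suspending trial to monitor > 25% targeted AE". Its first two rows read "Suspend if number of AEs >7/20" and "Suspend if number of AEs >13/40"; the third sets the limit at more than 25 of 80. The true rates tabulated are 0.20, 0.25, 0.30 and 0.35.

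The Protocol Summary (Human Subjects row) says: "Side effects are anticipated to be mild and limited to reversible orthostatic/postural hypotension and transient increases in creatinine".

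No section gives an expected or background rate for the targeted toxicities, or a reason for 25%. Sections 10.4 to 10.6 contain no between-arm toxicity analysis, and the table in 10.8 marks every objective N under Safety.

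**The concern.** The counted events are severe, yet suspension needs 40%, 35% or 32.5% of intensive-arm patients to have one. The lowest rate tabulated is 20%, so a reader cannot see how the rule behaves at rates closer to what the Summary leads one to expect.

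Whether intensification is safe is a question about the difference between arms. The rule uses only one arm, although a randomised standard arm runs alongside. A high count could be chemotherapy toxicity, and a moderate count could be a large excess over the standard arm. The rule cannot tell these apart.

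At stake is late recognition of severe renal or syncopal harm in children and young adults assigned to a deliberately lower blood pressure.

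**Working it through.** **Inputs from 10.3.** The limits are >7/20, >13/40 and >25/80. Read strictly, the lowest suspending counts are 8/20 = 40%, 14/40 = 35% and 26/80 = 32.5%. The text says number of AEs; the binomial design implies patients with an event.

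**Method.** Let X(n) be the number of patients with an event among the first n, binomial with true rate p. The stage-wise probability of suspension is the chance of first crossing at that look, with paths that crossed earlier removed:

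- look 1: P[X(20) >= 8]
- look 2: P[X(20) <= 7 and X(40) >= 14]
- look 3: P[X(20) <= 7, X(40) <= 13 and X(80) >= 26]

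**Reproducing the printed table.**

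| True rate | Printed | Exact | Exact total |
|---|---|---|---|
| 0.20 | 0.03 / 0.01 / 0.00 | 0.032 / 0.011 / 0.003 | 4.5% |
| 0.25 | 0.07 / 0.03 / 0.01 | 0.102 / 0.053 / 0.032 | 18.7% |
| 0.30 | 0.23 / 0.14 / 0.12 | 0.228 / 0.136 / 0.118 | 48% |
| 0.35 | 0.40 / 0.22 / 0.18 | 0.399 / 0.217 / 0.177 | 79% |

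Three columns agree within one point, which confirms the strict reading and the first-crossing definition. Limits one lower or one higher do not match. The 0.25 column, the rate the rule is built around, does not reproduce: printed total 0.07 + 0.03 + 0.01 = 11%, exact 18.7%. It should be corrected, but the argument here does not depend on it.

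**Below the tabulated range** (illustrative rates, not in the documents).

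- 10%: total 0.04%.
- 15%: 0.0059 + 0.0008 + 0.00003 = 0.0068 before rounding the terms, or 0.7%.

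**A between-arm trigger.** At 20 and again at 40 patients per arm, suspend and investigate if the one-sided Fisher exact p for an excess in the intensive arm is <=0.10. The probabilities below are exact over both looks, with first-look crossings removed before the second. All standard-arm rates are assumptions.

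| Intensive vs standard | New trigger, looks at 20 and 40 per arm | Present rule, all three looks |
|---|---|---|
| 15% vs 2% | 67% | 0.7% |
| 15% vs 5% | 45% | 0.7% |
| 20% vs 5% | 71% | 4.5% |
| 20% vs 10% | 42% | 4.5% |
| 15% vs 10% | 21% | 0.7% |

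False alarms over both looks at equal rates: 0.4% at 2%, 2.6% at 5%, 6.1% at 10%, 8.2% at 15%.

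**The case against.** **A ceiling is not a forecast.** The Summary describes expected side effects of antihypertensives. Section 10.3 sets a limit on all-cause events in patients who also receive leukaemia chemotherapy, and 4.1 recognises kidney injury and hypotension from other causes. A reader might infer that the two passages contradict each other. They do not: they are in tension, because nothing in the plan connects an expectation of mild, reversible effects to a 25% ceiling for severe ones.

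**Rare suspension at 15% is what a rule aimed at rates above 25% should do.** This stands. The 10% and 15% scenarios show how the rule behaves and are not a malfunction. Which rate is acceptable is a clinical judgement.

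**Some large excesses would be caught.** A reader might infer that a several-fold excess would pass every look. That depends on a background rate the documents do not give. Over an assumed 5%, a six-fold excess (30%) suspends with 48% probability and a seven-fold excess (35%) with 79%.

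**Other oversight exists.** Section 9.1 provides at least monthly toxicity summaries to the PI and Biostatistics, 9.2 a monitor's report to the Internal Monitoring Committee, 8.1 unanticipated-problem reporting that covers unexpected frequency, and 7.2 individual off-therapy criteria. So it would be wrong to infer that the trial could not otherwise be paused. None of these, however, sets a numerical trial-level threshold.

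**A background allowance does not rescue a single-arm count.** If 25% allows for chemotherapy toxicity, then with a low background the limit is loose, and with a high one the count cannot be attributed to the lower target. Either way the standard arm is needed.

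**Conclusion.** The point holds as a worthwhile, low-cost safety improvement. The suspension probabilities follow exactly from the plan's own limits. So does the structural weakness: one arm is counted for a between-arm question, against a ceiling with no stated basis.

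That the rule would usually miss a several-fold excess rests on an assumed low standard-arm rate. With 2% or 5% in the standard arm and 15% in the intensive arm, the chance of suspension is 0.7%. That a single-arm count cannot separate chemotherapy toxicity from harm due to the lower target needs no such assumption.

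The documents do not show that 25% is wrong. They only fail to say why it was chosen.

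**What to change.** 1. In 10.3, state the basis for 25%, including the background rate assumed, and reconcile it with the Human Subjects row of the Protocol Summary. The acceptable rate stays with the clinical team.
2. Keep the present limits as a backstop.
3. Count the same targeted events in both arms over the same phases. Section 9.1 already records non-hematologic grade 3-5 events in glucocorticoid phases without restriction by arm. Syncope with injury should be named on the form, since 10.3 defines it by injury and not by grade.
4. Add a suspend-and-investigate trigger at 20 and 40 patients per arm: one-sided Fisher p<=0.10 for an excess in the intensive arm.
5. Extend the printed table to rates below 20% and correct the 0.25 column.

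The cost is wording in 10.3, one item on the form, and the false-alarm risk shown above, which rises with the background rate. Each alarm leads to a pause for investigation and not to termination. Two limits should be stated openly: small differences such as 15% vs 10% are detected only 21% of the time, and after 40 per arm only the present rule remains.

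### Section 10.3: the third look of the target-attainment rule counts failures where successes are meant, which reverses it, and five printed suspension probabilities do not reproduce

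*Combined protocol and SAP*

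**What the plan says.** Section 10.3 sets three monitoring rules for the intensive arm, built on a binomial group sequential design with looks at 20, 40 and 80 patients. The consequence of a crossing is explicit: "We shall suspend the trial and investigate if any threshold defined in the rules is crossed".

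- **Adverse-event rule**, introduced as "Probabilities of suspending trial to monitor > 25% targeted AE". The boundaries are "Suspend if number of AEs >7/20", "Suspend if number of AEs >13/40" and "Suspend if number of AEs >25/80".
- **Target-attainment rule**, introduced as "Monitoring of missing the target in the intensive treatment arm: against <70"%. Look 1 suspends on fewer than 12 successes in 20. Look 2 is "Suspend if number of successes <24/40". Look 3 is "Suspend if number of failures <51/80". The columns are headed by true success probability: 0.55, 0.60, 0.70 and 0.75.
- **MRI efficacy rule**, which suspends on fewer than 7/20, 16/40 or 33/80 successes.

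The three tables print 39 suspension probabilities (12, 12 and 15). No other section restates or corrects the look-3 row.

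**The concern.** The attainment rule exists to catch an arm that misses its target, and its first two looks trigger on low success counts. The third triggers on a low failure count, which is the opposite direction. Because the section makes every threshold an instruction to suspend, whoever applies look 3 must either follow a reversed rule or depart from the text.

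Separately, the tables are the only statement of how often each rule would suspend the trial. If cells are wrong, readers of the plan have been misinformed about those rates. This matters most in the 0.25 column of the adverse-event table, which is that rule's own limit.

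**Working it through.** **Inputs.** Boundaries, looks and printed probabilities are all from section 10.3.

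**Method.** Let S(n) be the number of events (adverse events or successes) among the first n patients, binomial with true probability p. The probability for look j is that of crossing for the first time there:

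P(j) = P(no crossing at looks 1 to j−1, and S(n_j) crosses its boundary).

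This is computed exactly by carrying the distribution of S forward from 20 to 40 to 80 and removing crossed paths at each look.

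**Step 1: does this reproduce the plan?** For the MRI rule, all 15 cells agree to two decimals. At 0.35, for example, it gives 0.417, 0.307, 0.170 against 0.42, 0.31, 0.17 printed. The adverse-event rule at 0.20, 0.30 and 0.35 reproduces all nine cells. At 0.30 it gives 0.228, 0.136, 0.118 against 0.23, 0.14, 0.12 printed. The printed figures are therefore first-crossing probabilities with strict inequalities.

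**Step 2: look 3 of the attainment rule.** Failures < 51 means failures ≤ 50, so successes ≥ 80 − 50 = 30, or 37.5% and above.

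| True success probability | 0.55 | 0.60 | 0.70 | 0.75 |
|---|---|---|---|---|
| Printed look 3 | 0.19 | 0.24 | 0.04 | 0.00 |
| Successes < 51 | 0.191 | 0.236 | 0.045 | 0.005 |
| Failures < 51, as written | 0.245 | 0.461 | 0.861 | 0.954 |
| Total over three looks, successes < 51 | 0.946 | 0.775 | 0.184 | 0.051 |
| Total over three looks, as written | about 1.00 | about 1.00 | about 1.00 | about 1.00 |

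The printed row was computed for successes. As written, a trial that has passed look 2 with at least 24/40 escapes suspension only if it ends at 24 to 29 of 80, that is, with at most 5 of the next 40 at target. That path has probability about 2 in 10^9 at 0.55 and less at the higher rates.

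**Step 3: cells that fail.**

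| Table and cell | Printed | Computed |
|---|---|---|
| Adverse events, 0.25, look 1 | 0.07 | 0.102 |
| Adverse events, 0.25, look 2 | 0.03 | 0.053 |
| Adverse events, 0.25, look 3 | 0.01 | 0.032 |
| Attainment, 0.70, look 2 | 0.07 | 0.025 |
| Attainment, 0.75, look 2 | 0.03 | 0.005 |

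The first of these needs no sequential calculation: P(X > 7) for X binomial(20, 0.25) is 0.102.

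With the look-3 word corrected, the other 34 cells agree within 0.006.

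**Step 4: could the boundaries be wrong instead?** For attainment look 2, among boundaries <20 to <31, only <24 gives the printed 0.17 and 0.13 at 0.55 and 0.60. That same boundary gives 0.025 and 0.005 at 0.70 and 0.75. For adverse events, no set with look 1 from >5 to >10, look 2 from >10 to >17 and look 3 from >20 to >31 gives 0.07, 0.03, 0.01 at 0.25 (each within 0.006). Marginal, cumulative and conditional probabilities, and non-strict inequalities, do not rescue the five cells either.

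**Step 5: effect on totals.** The plan prints no totals, so these are sums of its cells.

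- Adverse events at 0.25: 0.07 + 0.03 + 0.01 = 0.11 printed, 0.187 computed.
- Attainment at 0.70: 0.11 + 0.07 + 0.04 = 0.22 printed, 0.184 computed.
- Attainment at 0.75: 0.04 + 0.03 + 0.00 = 0.07 printed, 0.051 computed.

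**The case against.** **Nobody would apply the row literally.** The table's title, its column heading, the wording of looks 1 and 2 and the falling look-3 probabilities all point to successes. A literal reading would cause needless suspension and would almost never miss a failing arm. This is fair and limits the consequence. It does not remove the error from an operative threshold.

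**No action depends on the five cells.** Suspension is triggered by counts, which stay as they are. The adverse-event rule suspends more readily at 25% than printed, so the misprint does not weaken protection of participants. That also stands. The cells are a matter of accurate reporting.

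**The fault may lie in the headings.** Under the printed boundaries, attainment look 2 gives 0.073 at a true rate of 0.65 and 0.025 at 0.70. The printed 0.07 and 0.03 would therefore fit a row shifted by one column after a 0.65 column was dropped. The adverse-event figures fit a true rate near 0.23 (0.068, 0.031, 0.014). Both are plausible and worth checking against the source output. They concern the cause only: under the headings as printed, the values are wrong.

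**A sixth cell is off.** Attainment look 3 at 0.70 computes to 0.0451 and is printed as 0.04. That is a difference of rounding size, within the 0.006 agreement used here.

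**Conclusion.** The concern holds. Look 3 of the attainment rule is reversed by one word. As written, it makes suspension by the third look practically certain at every true rate tabulated, where the intended rule gives 0.946, 0.775, 0.184 and 0.051. Five of 39 printed probabilities are wrong under their headings. The largest effect on a total is at the adverse-event rule's own 25% limit, where the chance of suspending is 0.187 and the printed cells imply 0.11.

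The error should be fixed but is not grave. The intent is recoverable, a crossing means suspend and investigate, and look 3 falls at 80 intensive-arm patients when about 180/2 = 90 are to be randomized to that arm (section 10.1). The result assumes independent patients with a common true rate and first-crossing probabilities at 20, 40 and 80. The 34 matching cells confirm that these are the plan's own assumptions.

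**What to change.** In section 10.3:

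1. Change the look-3 row of the attainment table to suspend when the number of successes is below 51/80 (equivalently, failures above 29/80).
2. Reprint look 2 of that table as 0.03 at 0.70 and 0.00 at 0.75 (0.025 and 0.005).
3. Reprint the 0.25 column of the adverse-event table as 0.10, 0.05, 0.03 (0.102, 0.053, 0.032).

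While the tables are open, check the column headings against the original output, and round attainment look 3 at 0.70 to 0.05. One line defining a success for this count would also help. The cost is one word and five cells. No threshold, sample size or conduct changes.
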